8 STATISTICAL CONSIDERATIONS

8.1 Study Endpoints

8.1.1 Primary endpoint: Establish efficacy of study regimen by showing that at least 33% of patients will achieve at least a 30 percent decrease in VAS pain score from baseline to the end of week 9 of treatment and follow-up period. Earlier studies have shown that the VAS pain score ($\geq 4/10$) on the day of treatment initiation can be used as baseline in this setting and a 30% or higher reduction in baseline pain score is a sign of meaningful drug response.(27-29)

8.1.2 Secondary endpoint:

1. Monitor compliance of study drug regimen through OM Pain App and medication diary.

2. Identify study participants who require off-protocol opioids for pain control despite being on the highest dose of study drug combination.
3. Correlate cumulative mean weekly pain scores calculated by the pain app with the average weekly pain scores recorded by the BPI short form.
4. Correlate average weekly OM Pain App scores and average weekly pain scores calculated from the BPI short form with head and neck symptoms and function evaluation tool MDASI-HN. The cumulative average area under the curve (AUC) weekly pain scores are expected to be inversely proportion to MDASI-HN average weekly AUC physical activity scores.
5. Maintain a weekly log of use of other nonopioid supportive care medications, such as laxatives, antiemetics, and oral anesthetics, in conjunction with the study drug combination during treatment and follow-up period through weekly questionnaires. Average weekly use of laxatives and antiemetics is expected to decrease by the end of follow up period.
6. Assess incidence and severity of gastrointestinal and cognitive side effects of the study drug regimen and their impact on quality of life, as measured by weekly PROMIS® (GI and cognition) questionnaires.
7. Safety: Assess the incidence and severity of other adverse events associated with the study drug combination using CTCAE version 5.

8.2 Study Design

This is a single-arm prospective clinical trial to determine the safety and feasibility of using transdermal buprenorphine in alleviation of radiation-induced mucositis pain in head and neck cancer patients with 12-week follow-up.

8.3 Study populations

- The enrolled population will consist of all enrolled patients. This population will be used in the CONSORT diagram, and patient disposition summaries.
- The treated population will consist of all enrolled patients who received at least one dose of the study medication. This population will be used for the efficacy and safety analyses.
- The per-protocol population will consist of all treated patients whose treatment followed without major protocol violations. This population will be used for sensitivity analyses.

8.4 Determination of Sample Size and Accrual Rate

Based on earlier studies (48) and the IMMPACT recommendations(28), a 30% or higher decrease in pain score from baseline to the end of the follow-up period is a sign of clinically meaningful efficacy of the drug regimen within a patient. A randomized trial of pregabalin for the treatment of radiotherapy-related pain in head-and-neck cancer patients (33) observed an at least 30% decrease in 33% of placebo-treated patients. This study will use a single-stage design to evaluate the hypothesis that patients treated with buprenorphine will achieve at least a 30% decrease in pain with probability exceeding 33%. Formally, the following hypotheses will be evaluated at a one-sided 5% significance level:

$$H_0: p (\geq 30\% \text{ decrease}) = 0.33 \quad \text{versus} \quad H_a: p (\geq 30\% \text{ decrease}) > 0.33.$$

With 18 subjects, the study will have at least 80% power to reject the null hypothesis if the probability of achieving at least 30% decrease in pain with buprenorphine is, in fact, 63%. The hypothesized effect is consistent with the efficacy seen with other active treatments. Specifically,

buprenorphine will be considered an acceptable pain control medication if 10 or more subjects out of the 18 experience at least 30% pain reduction. We will enroll 20 subjects to allow for 10% drop-out rate.

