5.2 Dose Determination for Buprenorphine and Tramadol

Based on our clinical experience and earlier studies barring exceptions, the typical MEDD dose of standard-of-care regimens, such as oxycodone, morphine and fentanyl patch used in the treatment of radiation-induced mucositis can range from 20 to 90 mg. Buprenorphine is a potent opioid substitute but there is no consensus at equipotency ratio for morphine to transdermal buprenorphine. Some authors have reported that it lies somewhere between 75:1 to 100:1.(34) This makes finding the appropriate morphine equivalent daily dose (MEDD) for buprenorphine in controlling mucositis-related pain a challenging task. For our study, we used 75:1 equipotency ratio to calculate our morphine equivalent daily dose (**Table 1**). As transdermal buprenorphine is a long-acting medication, we plan to allow tramadol 50 mg (total daily dose) as needed for breakthrough pain up to 400 mg/day (total daily dose), which roughly translates to 5 mg to 40 mg MEDD. Steady-state plasma buprenorphine concentration levels are achieved by day 3, during the first application of buprenorphine. Therefore, it can be titrated after a minimum of 72 hours. We hope to evaluate the possibility of using tramadol to facilitate dose adjustment of buprenorphine. With the buprenorphine and tramadol combination, we hope to provide MEDD to patients which is comparable to other standard-of-care opioids. There is no clear consensus definition of adequate and inadequate pain relief in this setting. However, it is well known that a VAS pain score of $\leq 3/10$ is considered mild intensity pain in multiple settings. Based on some earlier studies and the titratability of TD buprenorphine dose, we have defined adequate analgesia as VAS $\leq 3/10$ for 72 hours, inadequate analgesia as VAS $> 3/10$ for 72 hours, and unbearable pain as VAS $> 3/10$ for 96 hours.(16, 17) If patients have unbearable pain (VAS $> 3/10$ x 96 hours) despite being on highest dose of the buprenorphine patch and tramadol, then, we will switch from tramadol to oxycodone for breakthrough pain and continue treatment with buprenorphine. We will titrate this combination as needed for pain control until study completion. Some authors have also shown the benefit and safety of using immediate-release oxycodone in conjunction with transdermal buprenorphine for moderate to severe pain.(35) If the pain is still uncontrolled $> 3/10$ for 72 hours, even after using oxycodone 90 mg/day with buprenorphine 20 μ g/hour, then, the patient will be taken off the study regimen. However, data monitoring will continue. Patients suffering intolerable side effects (severe constipation, vomiting, headache, pruritis, sedation, or respiratory depression, etc.) or those who wish to switch to standard-of-care oxycodone due to ineffective pain control or unclear reasons at any time during the study will be taken off study regimen. However, data monitoring through the pain app and questionnaires will continue. The dose titration schedule is illustrated in **Table 2**.

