
5.3 Morphine Daily Dose Equivalent of TD Buprenorphine

Table 1:	
Buprenorphine patch	Morphine equivalent daily dose
5 mcg/hr	9 mg
10 mcg/hr	18 mg
15 mcg/hr	27 mg
20 mcg/hr	36 mg

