5.4 Drug Regimen Titration Schedule

Table 2 Drug Titration Schedule

Drug: Buprenorphine with tramadol for breakthrough pain (**First seven weeks of study**) $T = 0 - 7$ weeks;

Start TD buprenorphine 5 μ g/hour along with oral tramadol 50 mg to 150 mg (total dose over 24 hours) as needed for breakthrough pain when mucositis related pain is $\geq 4/10$ on VAS measured on OM Pain App and BPI. Further dose adjustments will be made through pain app.

- If VAS is $>3/10$ for 72 hours on tramadol 150 mg (total dose over 24 hours) and buprenorphine 5 μ g/hour, then, increase tramadol to 250 mg (total dose over 24 hours).
- If VAS is $>3/10$ for 72 hours, even with tramadol 250 mg (total dose over 24 hours) and buprenorphine 5 μ g/hour, then, increase dose of buprenorphine to 10 μ g/hour.
- If the pain persists VAS $>3/10$ for 72 hours on tramadol 250 mg (total dose over 24 hours) and 10 μ g/hour, then, increase the dose of tramadol to 350 mg (total dose over 24 hours).
- If VAS pain is $>3/10 \times 72$ hours with both tramadol 350 mg (total dose over 24 hours) and buprenorphine 10 μ g/hour, then, increase dose of buprenorphine to 15 μ g/hour.
- If VAS pain $>3/10 \times 72$ hours on tramadol 350 mg (total dose over 24 hours) and 15 μ g/hour of buprenorphine, then, increase the dose of tramadol to 400 mg (total dose over 24 hours) and buprenorphine to 20 μ g/hour.
- If the pain persists and is unbearable at $>3/10$ for 96 hours, despite being on highest dose of both drugs, then, replace tramadol with oxycodone at the clinician's discretion up to 90 mg (total dose over 24-hour period) for pain relief.
- If VAS is $\leq 3/10$ maintained for 72 hours, then, we can start tapering off total daily tramadol dose by 50 mg every day, but not change the buprenorphine dose during the first seven weeks of treatment, as mucosal injury from ongoing radiation may increase pain later.

(Post-radiation period) $T = 8 - 12$ weeks: if necessary, increase dose of buprenorphine up to 20 mcg along with tramadol up to 400 mg/day as per titration schedule used in the first seven weeks until VAS is $\leq 3/10$. If pain is well controlled (VAS $\leq 3/10 \times 72$ hours), start weekly tapering of buprenorphine by 5 mcg and tramadol by 50 mg daily.

Special Circumstances

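### Sections 8.2 and 8.4 state the design, hypothesis, power and decision rule for buprenorphine alone, but the trial tests a co-titrated regimen and cannot attribute response to the patch

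*Combined protocol and SAP*

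**What the plan says.** Section 8.4 takes its null rate from an external trial that "observed an at least 30% decrease in 33% of placebo-treated patients" and states that "the following hypotheses will be evaluated at a one-sided 5% significance level". It frames the hypothesis for patients treated with buprenorphine, claims at least 80% power "if the probability of achieving at least 30% decrease in pain with buprenorphine is, in fact, 63" percent, and gives the decision rule: "buprenorphine will be considered an acceptable pain control medication if 10 or more subjects out of the 18 experience at least 30% pain reduction". Section 8.2 describes the design as one "to determine the safety and feasibility of using transdermal buprenorphine in alleviation of radiation-induced mucositis pain". None of these sentences mentions tramadol.

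Elsewhere the object is the combination. The Section 2 hypothesis and the primary objective (2.1) name buprenorphine with oral tramadol. The primary endpoint (2.4 and 8.1.1) concerns the efficacy of the study regimen. Section 8.7 describes the pilot as a study of the two-drug combination.

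Table 2 (Section 5.4) raises the two drugs alternately, tramadol first. The last up-titration step is to "increase the dose of tramadol to 400 mg (total dose over 24 hours) and buprenorphine to" 20 µg/hour. If pain persists at the highest doses, oxycodone up to 90 mg/day replaces tramadol while the patch continues. If that fails, the patch can come off.

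**The concern.** The pre-specified conclusion names one component of a treatment that every patient receives as a package. There is no control arm, both opioids are titrated to the same pain score, and Section 1.3 itself describes tramadol as acting synergistically with long-acting opioids. A count of responders under those conditions describes the package.

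At stake is what the trial may claim. Read literally, 10 responders would let the report call buprenorphine an acceptable analgesic when the design has no means of separating it from tramadol or, in some patients, oxycodone. The wording also leaves the statistical section at odds with the objective and endpoint it is meant to serve.

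**Working it through.** **1. The plan's own figures.** Inputs from Section 8.4: n = 18, cut-off 10, null rate 0.33, alternative 0.63, one-sided 5%. Exact binomial:

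- Alpha = P(X ≥ 10 | n = 18, p = 0.33) = 0.0405.
- Power = P(X ≥ 10 | n = 18, p = 0.63) = 0.8165.
- A cut-off of 9 would give alpha 0.102, so 10 is the smallest admissible cut-off.
- Enrolment: 18 / 0.90 = 20.

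The design arithmetic reproduces. The issue is only what the rule is said to show.

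**2. How large the second drug is.** Section 5.2 uses 75:1 for buprenorphine and says of tramadol 50 to 400 mg/day, "which roughly translates to 5 mg to 40 mg MEDD", which is a factor of 0.1. Table 1 (Section 5.3) lists the "Morphine equivalent daily dose" (MEDD) for each patch.

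- Buprenorphine MEDD = µg/h × 24/1000 × 75 = 9, 18, 27 and 36 mg for 5, 10, 15 and 20 µg/h. This reproduces Table 1.
- Tramadol MEDD = 0.1 × mg/day.
- Tramadol share = tramadol MEDD / (tramadol MEDD + buprenorphine MEDD).

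Section 5.2 also cites 100:1 as the other end of the reported range. At that ratio the patch values become 12, 24, 36 and 48 mg.

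| Up-titration pair in Table 2 | Share at 75:1 | Share at 100:1 |
|---|---|---|
| 5 µg/h + 150 mg | 15/24 = 62.5% | 15/27 = 55.6% |
| 5 µg/h + 250 mg | 25/34 = 73.5% | 25/37 = 67.6% |
| 10 µg/h + 250 mg | 25/43 = 58.1% | 25/49 = 51.0% |
| 10 µg/h + 350 mg | 35/53 = 66.0% | 35/59 = 59.3% |
| 15 µg/h + 350 mg | 35/62 = 56.5% | 35/71 = 49.3% |
| 20 µg/h + 400 mg | 40/76 = 52.6% | 40/88 = 45.5% |

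**3. Where the share is lower (75:1).**

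- At the bottom of the starting range, 5 µg/h + 50 mg: 5/14 = 35.7%. The break-even with the 5 µg/h patch is 90 mg (9/18 = 50%), inside the 50 to 150 mg starting range.
- During the taper, for example 20 µg/h + 300 mg: 30/66 = 45.5%. In the first seven weeks tramadol may fall by 50 mg each day with the patch unchanged, so 400 mg could reach zero in 400/50 = 8 days.
- After oxycodone replaces tramadol: 0%.

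**4. Who can be counted.** Section 8.3 analyses efficacy in all treated patients. Section 8.6 asks for at least two weeks on the regimen for evaluability. Section 5.2 continues data monitoring after a patient leaves the regimen. No section says how a week-9 responder who is taking oxycodone, or is off the patch, counts toward the 10. Section 5.1 expects about 20% to need rescue: 0.20 × 18 = 3.6 patients, against a cut-off of 10. How many of those would also be responders cannot be known from the documents.

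**The case against.** The strongest reply is that *buprenorphine* in Sections 8.2 and 8.4 is shorthand matching the trial's title. The regimen is the named object almost everywhere else, Section 8.4 itself opens by speaking of the drug regimen, the binomial test in Section 8.6 names no drug, and no section claims to separate the patch from tramadol. This is fair as to intent. It does not rescue the text, because the single-drug wording runs through the design, hypothesis, power and decision sentences, and the last of these is the only success rule in the plan.

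The second reply concerns the shares. A reader might infer from the table that tramadol supplies more than half of the opioid equivalent at every step of Table 2, or that any observed response would be mostly tramadol. The documents do not support either. Step 3 shows the exceptions. Tramadol is taken as needed while the patch is continuous, so the shares apply only if the full named dose is taken. Section 5.2 calls the tramadol conversion rough and says there is no agreed buprenorphine ratio. Well-controlled patients may have tapered tramadol before the week-9 reading. This part of the objection stands, and the shares show only that the second drug is not negligible.

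A reader might also infer that a positive count would trigger follow-on work on the wrong drug. The documents contain no such rule. Section 8.7 speaks only of pilot data for future studies.

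**Conclusion.** The wording of Sections 8.2 and 8.4 is wrong as written. It conflicts with the objective, the endpoint and Section 8.7, and a single-arm count on two co-titrated opioids cannot support a conclusion about one of them. This rests on the design alone and does not depend on any conversion ratio or on tramadol exceeding half of the total.

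As to size, tramadol would be 52.6% to 73.5% of MEDD at the six up-titration pairs, assuming the full named dose is taken, 75:1 for buprenorphine and 0.1 for tramadol. At 100:1 the range is 45.5% to 67.6%. The share actually taken at week 9 is unknown. The error is in the stated inference and not in the test: n = 18, the cut-off of 10, alpha 4.05% and power 81.6% are all sound.

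**What to change.** - In Sections 8.2 and 8.4, replace *buprenorphine* in the design, hypothesis, power and decision sentences with: the study regimen (transdermal buprenorphine plus oral tramadol, with oxycodone substitution as allowed in Table 2). A label naming only buprenorphine and tramadol would misdescribe patients moved to oxycodone.
- Add one sentence saying that response cannot be attributed to any single component.
- Beside the primary result, tabulate from the drug diary each patient's week-9 buprenorphine, tramadol and oxycodone use by response, and report how many responders were on oxycodone or off the patch. Section 8.6 now plans only the number of patients using analgesics, without dose and not by response.

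The diary data are already collected (Section 5.12), so the cost is a few words, one descriptive table and a slightly narrower claim. The sample size, the cut-off and the test do not change, and no dose or clinical rule is affected.

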8.5 Feasibility

We will be able to complete protocol development and receive IRB approval in two months. Based on our previous experience, we normally see around 64 stage II-IV HNSCC patients annually who fulfill the eligibility criteria of the study. During 12 months of the potential accrual period, we will be able to contact 25 subjects. Under an assumed 80% consent rate, 19 to 20 subjects will be enrolled into the study. Assuming a 10% dropout rate, we will end up with around 18 patients participating in our study. Since close to 100% patients develop mucositis and develop at least moderate intensity pain requiring opioid medications through radiation therapy, we do not anticipate any screen failures. However, if a screen failure occurs for some reason then we plan to replace those patients to ensure an evaluation of 18 patients. Patients will be followed for 12 weeks. Final interpretation of pain app data, standardized measurement tools and document of results will be done in the last month of the study period. We are confident of completing the accrual in 12 months.

8.6 Data Analysis

Serial measurements of patient-reported pain data will be analyzed throughout the follow-up period to look for inadequate pain control and use of off-protocol breakthrough pain medication use. The pain app data will be analyzed by study coordinators and our collaborators at UWM. Data recording will commence on the day the patient starts taking the drug regimen. We plan to study the daily and weekly pain score patterns during therapy. We will determine the baseline VAS pain score on the day of treatment initiation. Other pain management studies in radiation-induced mucositis acknowledged the fact that the pain curve follows a nonlinear pattern during radiation therapy, but it plateaus and later drops down to a lower level after initiation of long-acting effective pain medications. Hence, it is reasonable to use the pain score on the day of treatment initiation as our baseline pain score. (29, 31) Radiation-induced mucositis begins to heal approximately two weeks after the last dose of stomatotoxic chemotherapy or radiation therapy.(30, 32) We will assess a percentage drop in the pain score by the end of week 9 of treatment to show a drug response. This way, we will try to avoid any bias of the normal healing process on pain alleviation. At least two-week treatment with study drug regimen will be required in order to be considered evaluable for study endpoints. Earlier studies and consensus guidelines have shown that a 30% drop in average weekly pain score by end of the follow-up period is significant. (28). The recording of data will cease after 12 weeks, at which time mucositis-related pain symptoms substantially abate in many individuals. (32)

The primary analysis will compare the proportion of patients achieving a 30% drop in pain scores to the null-hypothesis value of 33% at a one-sided 5% significance level using a binomial test. The number of patients using analgesic and non-analgesic medications, as well as the occurrence of adverse events, will be tabulated and presented as counts with percentages. The average weekly pain scores, MDASI-HN, and the PROMIS® measures will be reported with descriptive statistics (mean, standard deviation, median, and range). Patient level summaries of the pain score and PRO outcomes will be created by computing area under the curve (AUC) of weekly averages. Scatterplots will be used to explore their relationship which will be quantified by Spearman's correlation coefficient. Further correlational analysis will be done by linear regression and linear fixed models.

8.7 Rationale for not Having a Stopping Rule: This is a supportive care pilot study to determine

the efficacy of transdermal buprenorphine and oral tramadol drug combination in alleviating radiation-induced mucositis pain in head and neck cancer patients. These pain medications are FDA approved and have an established safety profile. In addition to the primary efficacy endpoint, we will be evaluating other secondary end points, such as real-time pain monitoring through the OM Pain App. This will continue, even if the study drug regimen is discontinued for lack of efficacy or some other unspecified reason. This would provide us invaluable pilot data for future studies in this setting. Moreover, we have made provisions for switching to standard-of-care pain medications, such as oral oxycodone in our study for patients who don't derive adequate pain relief from the study regimen. Hence, it is reasonable to exclude a formal stopping rule for this trial.

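### Sections 8.3 and 8.6 give different sets for the efficacy analysis, and how patients who stop within two weeks are counted can decide the primary test

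*Combined protocol and SAP*

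**What the plan says.** Section 8.3 defines three sets. Of the middle one it says: "The treated population will consist of all enrolled patients who received at least one dose of the study medication". The next sentence gives its use: "This population will be used for the efficacy and safety analyses". The only restricted set in that section, the per-protocol population, is kept for sensitivity analyses. Section 8.3 defines no evaluable population.

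Section 8.6 adds a different condition: "At least two-week treatment with study drug regimen will be required in order to be considered evaluable for study endpoints". The same section says that the primary analysis will "compare the proportion of patients achieving a 30% drop in pain scores to the null-hypothesis value of 33" per cent with a one-sided 5% binomial test. It does not say in which patients.

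Section 8.4 states the decision rule for one denominator only: success is "10 or more subjects out of the 18 experience at least 30% pain reduction". Twenty are enrolled to allow for 10% drop-out, and 8.5 expects that "19 to 20 subjects will be enrolled into the study". Section 4.11 does not replace treated patients who leave.

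Section 5.2 takes off the regimen, at any time, patients with intolerable side effects and "those who wish to switch to standard-of-care oxycodone due to ineffective pain control". It then adds: "However, data monitoring through the pain app and questionnaires will continue". Sections 4.11 and 8.7 also continue follow-up after the regimen stops. Section 8.8 handles missing data by multiple imputation under a missing-at-random assumption.

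**The concern.** A patient dosed for ten days belongs to the efficacy set under 8.3 and is not evaluable under 8.6. The primary endpoint is a study endpoint, so the conflict reaches the primary test.

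Leaving the regimen early is not always unrelated to the result. Intolerance and a chosen switch for poor pain control (5.2) are related to how the regimen performed. Intercurrent illness, noncompliance, need for a non-permitted therapy and investigator judgment (4.11) may or may not be. Section 5.4 also holds the regimen when a patient is admitted for intravenous pain medication. A set restricted to those who stayed two weeks may therefore have a different response rate from the set of all treated patients.

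Some early stoppers will have a week-9 score, because follow-up continues, and the plan does not say whether that score counts. In a trial of 20 with a formal cut-off, one or two patients can settle the decision.

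**Working it through.** **Inputs.** Null rate 0.33, one-sided 5%, alternative 0.63, cut-off 10 of 18, 20 enrolled, 10% drop-out (all 8.4). Early-stopping rates and stopper response rates are assumptions; the documents give neither.

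**The plan's own figure.** With X ~ Bin(18, p): P(X ≥ 10 | 0.33) = 0.0405 and P(X ≥ 10 | 0.63) = 0.816. A cut-off of 9 would have a type I error of 0.102. The design reproduces, and 18/0.9 = 20.

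**Exact cut-off by number analysed** (smallest k with P(X ≥ k | n, 0.33) ≤ 0.05):

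| n | cut-off | type I error | power at 0.63 |
|---|---|---|---|
| 17 | 10 | 0.0254 | 0.732 |
| 18 | 10 | 0.0405 | 0.816 |
| 19 | 11 | 0.0223 | 0.760 |
| 20 | 11 | 0.0350 | 0.835 |

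**Reversal, if early stoppers count as non-responders.** Ten responders give p = 0.0405 of 18, 0.0608 of 19 and 0.0866 of 20. Eleven responders pass in each case (0.0133 of 18, 0.0223 of 19, 0.0350 of 20). Nine fail even of 18 (0.102). So with 18 evaluable and one or two such stoppers, the sets disagree only at exactly 10 responders. With 20 treated and one such stopper, the evaluable set has 19, both sets need 11, and they always agree.

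**How often the sets disagree.**
- Exactly two of 20 stop early without responding, and the other 18 respond at 63%: C(18,10) × 0.63^10 × 0.37^8 = 0.151.
- Each of 20 treated stops early with probability 5% and never responds, and the others respond at 63%. Sum over s stoppers of P(s) × [P(X ≥ c(20−s)) − P(X ≥ 11)], with X ~ Bin(20−s, 0.63) and c(n) the exact cut-off. The terms for s = 0 and 1 are zero; s = 2 gives 0.1887 × 0.1514 = 0.0286; s = 3 gives 0.0596 × 0.1818 = 0.0108; s = 4 gives 0.0133 × 0.3722 = 0.0050. With the small remainder the total is about 0.045.

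**False success under the two-week rule, taking the all-treated rate as the target.** Assume 20 treated, a true all-treated rate of 0.33, a proportion d stopping early, and a stopper response rate r. The evaluable rate is then (0.33 − d·r)/(1 − d), and the cut-off is reset to the evaluable n. At d = 0.10:

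| stopper rate r | evaluable rate | false success |
|---|---|---|
| 0 | 0.33/0.90 = 0.367 | 6.5% |
| 0.165 (half) | 0.3135/0.90 = 0.348 | 4.6% |
| 0.33 (same) | 0.330 | 3.2% |

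The all-treated test, 11 of 20, has 3.5%.

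**The case against.** The strongest reply is that 8.3 already settles the matter: it assigns efficacy analyses to the treated population, and one sentence in 8.6 should not displace it. But that sentence is in the analysis section, covers the study endpoints and is not labelled as sensitivity. An analyst could follow either section.

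Four limits on the concern stand.

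- A reader might infer that the same data will pass under one section and fail under the other. The documents do not support that on their own. It needs early stoppers to be counted as non-responders, a rule in neither section (8.8 offers imputation), and, with up to two stoppers, exactly 10 responders of 18.
- A reader might take the 10% drop-out as two early stoppers. It is not split by timing. Enrolment can precede the first dose (3.2), and patients lost before dosing are in neither set. The 19 to 20 in 8.5 are enrolled patients, not dosed ones.
- A reader might suppose that the two-week rule removes mainly treatment failures. Several reasons in 4.11 are unrelated to pain response. Table 2 in 5.4 needs five steps of 72 hours plus 96 hours, or 19 days, before tramadol is replaced, so its uncontrolled-pain rule cannot act within two weeks. A late starter whose pain is controlled could even taper off early as a responder.
- The false-success figures take the all-treated rate as the target. That follows 8.3 but presupposes the answer to the question in dispute.

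These points limit the size and direction of the bias. They do not remove the conflict.

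**Conclusion.** The conflict between 8.3 and 8.6 is certain and should be fixed. The size of its effect is conditional. Bias is upward only if early stoppers respond less often than others, and the documents give no rate of stopping before two weeks.

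Under the least favourable response assumption (no early stopper responds), 10% early stopping raises false success to 6.5%. At half the overall response rate it stays below the nominal 5%. Disagreement between the sets ranges from none (20 treated, one stopper counted as a non-responder) through about 4.5% (random stopping at 5%) to 15.1% (exactly two non-responding stoppers). A reader might infer that the trial's type I error is necessarily inflated; these figures do not show that. They show that the primary decision can depend on a choice the plan has not made.

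**What to change.** In 8.6, name the treated population of 8.3 as the set for the primary binomial test, and use the two-week evaluable set only as a sensitivity analysis.

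State beforehand how dosed patients who stop before two weeks are classified:
- Use the week-9 score where it was collected.
- Without a week-9 score, count those who left for intolerance or lack of pain control as non-responders.
- Leave other missing scores to 8.8, and say how imputed data sets are combined into one test, since whole-number cut-offs do not apply to them directly.
- As sensitivity analyses, show the result with all early stoppers as non-responders, and with imputation under 8.8.

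In 8.4, give the exact cut-off for the number analysed: 10 for 17 or 18, and 11 for 19 or 20.

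No new data are needed. Power may fall: if 10% of treated patients stop early and fail while the rest respond at 63%, the overall rate is 0.90 × 0.63 = 0.567, and P(X ≥ 11 | 20, 0.567) is about 65%. In the other direction, week-9 scores taken after stopping may reflect other treatment or healing and so flatter the regimen. That is why the result with all early stoppers as non-responders should be shown beside the primary one.
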